14.1 Good Clinical Practice

The study will be conducted in accordance with the appropriate regulatory requirement(s). Essential clinical documents will be maintained to demonstrate the validity of the study and the integrity of the data collected. Master files should be established at the beginning of the study, maintained for the duration of the study and retained according to the appropriate regulations.

14.2 Ethical Considerations

The study will be conducted in accordance with ethical principles founded in the Declaration of Helsinki. The IRB will review all appropriate study documentation in order to safeguard the rights, safety and well-being of the patients. The study will only be conducted at sites where IRB approval has been obtained. The protocol, consent, written information given to the patients, safety updates, annual progress reports, and any revisions to these documents will be provided to the IRB by the investigator.

Appendix I – ECOG Performance Status

GRADE	ECOG PERFORMANCE STATUS
0	Fully active, able to carry on all pre-disease performance without restriction
1	Restricted in physically strenuous activity but ambulatory and able to carry out work of a light or sedentary nature, e.g., light house work, office work
2	Ambulatory and capable of all selfcare but unable to carry out any work activities; up and about more than 50% of waking hours
3	Capable of only limited selfcare; confined to bed or chair more than 50% of waking hours
4	Completely disabled; cannot carry on any selfcare; totally confined to bed or chair
5	Dead

Appendix II - Response Evaluation Criteria in Solid Tumors (RECIST) guideline (version 1.1)

Definitions:

Evaluable for Response: Only those patients who have measurable disease present at baseline, have received at least one cycle of therapy, and have had their disease re-evaluated will be considered evaluable for response. These patients will have their response classified according to the definitions stated below. (Note: Patients who exhibit objective disease progression prior to the end of cycle 1 will also be considered evaluable.)

Evaluable Non-Target Disease Response. Patients who have lesions present at baseline that are evaluable but do not meet the definitions of measurable disease, have received at least one cycle of therapy, and have had their disease re-evaluated will be considered evaluable for non-target disease. The response assessment is based on the presence, absence, or unequivocal progression of the lesions.

Disease Parameters:

Measurable disease. Measurable lesions are defined as those that can be accurately measured in at least one dimension (longest diameter to be recorded) as ≥ 20 mm by chest x-ray, as ≥ 10 mm with CT scan, or ≥ 10 mm with calipers by clinical exam. All tumor measurements must be recorded in millimeters (or decimal fractions of centimeters).

Note: Tumor lesions that are situated in a previously irradiated area might or might not be considered measurable. *If the investigator thinks it appropriate to include them, the conditions under which such lesions should be considered must be defined in the protocol.*

Malignant lymph nodes. To be considered pathologically enlarged and measurable, a lymph node must be ≥ 15 mm in short axis when assessed by CT scan (CT scan slice thickness recommended to be no greater than 5 mm). At baseline and in follow-up, only the short axis will be measured and followed.

Non-measurable disease. All other lesions (or sites of disease), including small lesions (longest diameter <10 mm or pathological lymph nodes with ≥ 10 to <15 mm short axis), are considered non-measurable disease. Bone lesions, leptomeningeal disease, ascites, pleural/pericardial effusions, lymphangitis cutis/pulmonitis, inflammatory breast disease, and abdominal masses (not followed by CT or MRI), are considered as non-measurable.

Note: Cystic lesions that meet the criteria for radiographically defined simple cysts should not be considered as malignant lesions (neither measurable nor non-measurable) since they are, by definition, simple cysts.

'Cystic lesions' thought to represent cystic metastases can be considered as measurable lesions, if they meet the definition of measurability described above. However, if non-cystic lesions are present in the same patient, these are preferred for selection as target lesions.

Target lesions. All measurable lesions up to a maximum of 2 lesions per organ and 5 lesions in total, representative of all involved organs, should be identified as **target lesions** and recorded and measured at baseline. Target lesions should be selected on the basis of their size (lesions with the longest diameter), be representative of all involved organs, but in addition should be those that lend themselves to reproducible repeated measurements. It may be the case that, on occasion, the largest

lesion does not lend itself to reproducible measurement in which circumstance the next largest lesion which can be measured reproducibly should be selected. A sum of the diameters (longest for non-nodal lesions, short axis for nodal lesions) for all target lesions will be calculated and reported as the baseline sum diameters. If lymph nodes are to be included in the sum, then only the short axis is added into the sum. The baseline sum diameters will be used as reference to further characterize any objective tumor regression in the measurable dimension of the disease.

Non-target lesions. All other lesions (or sites of disease) including any measurable lesions over and above the 5 target lesions should be identified as **non-target lesions** and should also be recorded at baseline. Measurements of these lesions are not required, but the presence, absence, or in rare cases unequivocal progression of each should be noted throughout follow-up.

Methods for Evaluation of Measurable Disease

All measurements should be taken and recorded in metric notation using a ruler or calipers. All baseline evaluations should be performed as closely as possible to the beginning of treatment and never more than 4 weeks before the beginning of the treatment.

The same method of assessment and the same technique should be used to characterize each identified and reported lesion at baseline and during follow-up. Imaging-based evaluation is preferred to evaluation by clinical examination unless the lesion(s) being followed cannot be imaged but are assessable by clinical exam.

Clinical lesions Clinical lesions will only be considered measurable when they are superficial (e.g., skin nodules and palpable lymph nodes) and ≥ 10 mm diameter as assessed using calipers (e.g., skin nodules). In the case of skin lesions, documentation by color photography, including a ruler to estimate the size of the lesion, is recommended.

Chest x-ray Lesions on chest x-ray are acceptable as measurable lesions when they are clearly defined and surrounded by aerated lung. However, CT is preferable.

Conventional CT and MRI This guideline has defined measurability of lesions on CT scan based on the assumption that CT slice thickness is 5 mm or less. If CT scans have slice thickness greater than 5 mm, the minimum size for a measurable lesion should be twice the slice thickness. MRI is also acceptable in certain situations (e.g. for body scans).

Use of MRI remains a complex issue. MRI has excellent contrast, spatial, and temporal resolution; however, there are many image acquisition variables involved in MRI, which greatly impact image quality, lesion conspicuity, and measurement. Furthermore, the availability of MRI is variable globally. As with CT, if an MRI is performed, the technical specifications of the scanning sequences used should be optimized for the evaluation of the type and site of disease. Furthermore, as with CT, the modality used at follow-up should be the same as was used at baseline and the lesions should be measured/assessed on the same pulse sequence. It is beyond the scope of the RECIST guidelines to prescribe specific MRI pulse sequence parameters for all scanners, body parts, and diseases. Ideally, the same type of scanner should be used and the image acquisition protocol should be followed as closely as possible to prior scans. Body scans should be performed with breath-hold scanning techniques, if possible.

PET-CT At present, the low dose or attenuation correction CT portion of a combined PET-CT is not always of optimal diagnostic CT quality for use with RECIST measurements. However, if the site can document that the CT performed as part of a PET-CT is of identical diagnostic quality to a diagnostic CT (with IV and oral contrast), then the CT portion of the PET-CT can be used for RECIST measurements and can be used interchangeably with conventional CT in accurately measuring cancer lesions over time. Note, however, that the PET portion of the CT introduces additional data which may bias an investigator if it is not routinely or serially performed.

Ultrasound Ultrasound is not useful in assessment of lesion size and should not be used as a method of measurement. Ultrasound examinations cannot be reproduced in their entirety for independent review at a later date and, because they are operator dependent, it cannot be guaranteed that the same technique and measurements will be taken from one assessment to the next. If new lesions are identified by ultrasound in the course of the study, confirmation by CT or MRI is advised. If there is concern about radiation exposure at CT, MRI may be used instead of CT in selected instances.

Endoscopy, Laparoscopy The utilization of these techniques for objective tumor evaluation is not advised. However, such techniques may be useful to confirm complete pathological response when biopsies are obtained or to determine relapse in trials where recurrence following complete response (CR) or surgical resection is an endpoint.

Tumor markers Tumor markers alone cannot be used to assess response. If markers are initially above the upper normal limit, they must normalize for a patient to be considered in complete clinical response. Specific guidelines for both CA-125 response (in recurrent ovarian cancer) and PSA response (in recurrent prostate cancer) have been published [JNCI 96:487-488, 2004; J Clin Oncol 17, 3461-3467, 1999; J Clin Oncol 26:1148-1159, 2008]. In addition, the Gynecologic Cancer Intergroup has developed CA-125 progression criteria which are to be integrated with objective tumor assessment for use in first-line trials in ovarian cancer [JNCI 92:1534-1535, 2000].

Cytology, Histology These techniques can be used to differentiate between partial responses (PR) and complete responses (CR) in rare cases (e.g., residual lesions in tumor types, such as germ cell tumors, where known residual benign tumors can remain).

The cytological confirmation of the neoplastic origin of any effusion that appears or worsens during treatment when the measurable tumor has met criteria for response or stable disease is mandatory to differentiate between response or stable disease (an effusion may be a side effect of the treatment) and progressive disease.

FDG-PET While FDG-PET response assessments need additional study, it is sometimes reasonable to incorporate the use of FDG-PET scanning to complement CT scanning in assessment of progression (particularly possible 'new' disease). New lesions on the basis of FDG-PET imaging can be identified according to the following algorithm:

- a. Negative FDG-PET at baseline, with a positive FDG-PET at follow-up is a sign of PD based on a new lesion.
- b. No FDG-PET at baseline and a positive FDG-PET at follow-up: If the positive FDG-PET at follow-up corresponds to a new site of disease confirmed by CT, this is PD. If the positive FDG-PET at follow-up is not confirmed as a new site of disease on CT, additional follow-up CT scans are needed to determine if there is truly progression occurring at that site (if so, the date of PD will be the date of the initial abnormal FDG-PET scan). If the positive FDG-PET at follow-up

corresponds to a pre-existing site of disease on CT that is not progressing on the basis of the anatomic images, this is not PD.

c. FDG-PET may be used to upgrade a response to a CR in a manner similar to a biopsy in cases where a residual radiographic abnormality is thought to represent fibrosis or scarring. The use of FDG-PET in this circumstance should be prospectively described in the protocol and supported by disease-specific medical literature for the indication. However, it must be acknowledged that both approaches may lead to false positive CR due to limitations of FDG-PET and biopsy resolution/sensitivity.

Note: A 'positive' FDG-PET scan lesion means one which is FDG avid with an uptake greater than twice that of the surrounding tissue on the attenuation corrected image.

Response Criteria

Evaluation of Target Lesions

Complete Response (CR): Disappearance of all target lesions. Any pathological lymph nodes (whether target or non-target) must have reduction in short axis to <10 mm.

Partial Response (PR): At least a 30% decrease in the sum of the diameters of target lesions, taking as reference the baseline sum diameters

Progressive Disease (PD): At least a 20% increase in the sum of the diameters of target lesions, taking as reference the smallest sum on study (this includes the baseline sum if that is the smallest on study). In addition to the relative increase of 20%, the sum must also demonstrate an absolute increase of at least 5 mm. (Note: the appearance of one or more new lesions is also considered progressions).

Stable Disease (SD): Neither sufficient shrinkage to qualify for PR nor sufficient increase to qualify for PD, taking as reference the smallest sum diameters while on study

Evaluation of Non-Target Lesions

Complete Response (CR): Disappearance of all non-target lesions and normalization of tumor marker level. All lymph nodes must be non-pathological in size (<10 mm short axis)

Note: If tumor markers are initially above the upper normal limit, they must normalize for a patient to be considered in complete clinical response.

Non-CR/Non-PD: Persistence of one or more non-target lesion(s) and/or maintenance of tumor marker level above the normal limits

Progressive Disease (PD): Appearance of one or more new lesions and/or *unequivocal progression* of existing non-target lesions. *Unequivocal progression* should not normally trump target lesion status. It must be representative of overall disease status change, not a single lesion increase.

Although a clear progression of "non-target" lesions only is exceptional, the opinion of the treating physician should prevail in such circumstances, and the progression status should be confirmed at a later time by the review panel (or Principal Investigator).

Evaluation of Best Overall Response

The best overall response is the best response recorded from the start of the treatment until disease progression/recurrence (taking as reference for progressive disease the smallest measurements recorded since the treatment started). The patient's best response assignment will depend on the achievement of both measurement and confirmation criteria.

For Patients with Measurable Disease (i.e., Target Disease)

Target Lesions	Non-Target Lesions	New Lesions	Overall Response	Best Overall Response when Confirmation is Required*
CR	CR	No	CR	>4 wks. Confirmation**
CR	Non-CR/Non-PD	No	PR	>4 wks. Confirmation**
CR	Not evaluated	No	PR	
PR	Non-CR/Non-PD/not evaluated	No	PR	
SD	Non-CR/Non-PD/not evaluated	No	SD	documented at least once >4 wks. from baseline**
PD	Any	Yes or No	PD	no prior SD, PR or CR
Any	PD***	Yes or No	PD	
Any	Any	Yes	PD	

* See RECIST 1.1 manuscript for further details on what is evidence of a new lesion.
 ** Only for non-randomized trials with response as primary endpoint.
 *** In exceptional circumstances, unequivocal progression in non-target lesions may be accepted as disease progression.

Note: Patients with a global deterioration of health status requiring discontinuation of treatment without objective evidence of disease progression at that time should be reported as "*symptomatic deterioration*." Every effort should be made to document the objective progression even after discontinuation of treatment.

For Patients with Non-Measurable Disease (i.e., Non-Target Disease)

Non-Target Lesions	New Lesions	Overall Response
CR	No	CR
Non-CR/non-PD	No	Non-CR/non-PD*
Not all evaluated	No	not evaluated
Unequivocal PD	Yes or No	PD
Any	Yes	PD

* 'Non-CR/non-PD' is preferred over 'stable disease' for non-target disease since SD is increasingly used as an endpoint for assessment of efficacy in some trials so to assign this category when no lesions can be measured is not advised

Duration of Response

Duration of overall response: The duration of overall response is measured from the time measurement criteria are met for CR or PR (whichever is first recorded) until the first date that recurrent or progressive disease is objectively documented (taking as reference for progressive disease the smallest measurements recorded since the treatment started).

The duration of overall CR is measured from the time measurement criteria are first met for CR until the first date that progressive disease is objectively documented.

Duration of stable disease: Stable disease is measured from the start of the treatment until the criteria for progression are met, taking as reference the smallest measurements recorded since the treatment started, including the baseline measurements.

Appendix III– Strong CYP3A4 Inducers

Most common strong CYP3A4 Inducers

Carbamazepine

Dexamethasone

Ethosuximide

Glucocorticoids

Griseofulvin

Phenytoin

Primidone

Progesterone

Rifabutin

Rifampin

Nafcillin

Nelfinavir

Nevirapine

Oxcarbazepine

Phenobarbital

Phenylbutazone

Rofecoxib (mild)

St John's wort

Sulfadimidine

Sulfinpyrazone

Troglitazone

Appendix IV – Potential Risks of Standard of Care Anti-PD1/PDL-1 Therapy

Source: Micromedex

Pembrolizumab

Common

- **Dermatologic:** Pruritus (11% to 28%), Rash, Immune-mediated (17% to 42%)
- **Endocrine metabolic:** Hypercholesterolemia (Non-small cell lung cancer, 20%), Hyperglycemia (40% to 48%), Hypertriglyceridemia (23% to 25%), Hypoalbuminemia (32% to 34%), Hyponatremia (10% to 38%)
- **Gastrointestinal:** Constipation (15% to 51%), Decrease in appetite (16% to 31%), Diarrhea (14% to 37%), Nausea (13% to 68%)
- **Hepatic:** Alkaline phosphatase raised (Non-small cell lung cancer, 26%), AST/SGOT level raised (20% to 24%)
- **Musculoskeletal:** Arthralgia (10% to 18%), Musculoskeletal pain (21% to 32%)
- **Respiratory:** Cough (15% to 24%), Dyspnea (11% to 39%)
- **Other:** Fatigue (20% to 71%)

Serious

- **Cardiovascular:** Vasculitis, Immune-mediated (Less than 1%)
- **Dermatologic:** Bullous pemphigoid (Less than 1%), Erythroderma (Less than 1%)
- **Endocrine metabolic:** Hypophysitis, Immune-mediated (0.6%)
- **Hematologic:** Anemia, Grade 3 or 4 (2% to 8%), Hemolytic anemia, Immune-mediated (Less than 1%)
- **Hepatic:** Hepatitis, Immune-mediated (0.7%), Pancreatitis, Immune-mediated (Less than 1%), Veno-occlusive disease of the liver, Immune-mediated (9%)
- **Immunologic:** Graft versus host disease, Immune-mediated (26%)
- **Musculoskeletal:** Eaton-Lambert syndrome, Rhabdomyolysis
- **Neurologic:** Confusional state (Head and neck cancer, 2% or more)
- **Ophthalmic:** Optic neuritis, Uveitis, Immune-mediated (Less than 1%)
- **Renal:** Nephritis, Immune-mediated (0.3%), Renal failure
- **Respiratory:** Pleural effusion (2% or more), Pneumonia (2% or more), Pneumonitis, Immune-mediated (3.4%), Respiratory failure (Head and neck cancer, 2% or more)
- **Other:** Infusion reaction (0.2%), Sepsis (Up to 10%)

Nivolumab

Common

- **Dermatologic:** Pruritus (10% to 28%), Rash
- **Endocrine metabolic:** Hyperglycemia (Urothelial carcinoma, 42%), Hyperkalemia (15% to 30%), Hypocalcemia (23% to 29%), Hyponatremia (25% to 41%), Serum cholesterol raised (Renal cell carcinoma, 21%), Serum triglycerides raised (Renal cell carcinoma, 32%)
- **Gastrointestinal:** Abdominal pain, Constipation (10% to 23%), Decrease in appetite (22% to 28%), Nausea (20% to 28%), Vomiting (12% to 28%)
- **Hematologic:** Anemia, All Grades (39% to 40%), Lymphocytopenia, All Grades (37% to 42%)
- **Hepatic:** Alkaline phosphatase raised (Urothelial carcinoma, 33%), ALT/SGPT level raised (Urothelial carcinoma, 18%), AST/SGOT level raised (Urothelial carcinoma, 24%)
- **Musculoskeletal:** Arthralgia (10% to 21%), Backache (Renal cell carcinoma, 21%), Musculoskeletal pain
- **Neurologic:** Asthenia, Headache (17% to 23%), Peripheral neuropathy (Up to 12%)
- **Renal:** Serum creatinine raised (Urothelial carcinoma, 39%)
- **Respiratory:** Cough (10% to 36%), Dyspnea (2% to 20%), Upper respiratory infection
- **Other:** Fatigue (49%)

Serious

- **Cardiovascular:** Myocarditis, Immune-mediated (Less than 1%), Vasculitis, Immune-mediated (Less than 1%)
- **Dermatologic:** Rash, Immune-mediated (9% to 22.6%), Stevens-Johnson syndrome, Immune-mediated, Toxic epidermal necrolysis, Immune-mediated
- **Endocrine metabolic:** Adrenal insufficiency, Immune-mediated (1% to 5%), Diabetic ketoacidosis, Hypercalcemia (Renal cell carcinoma, 19%), Hyperthyroidism, Immune-mediated (2.7% to 8%), Hypophysitis, Immune-mediated (0.6% to 9%), Hypopituitarism, Immune-mediated (Less than 1%), Hypothyroidism, Immune-mediated, Thyroiditis, Immune-mediated, Type 1 diabetes mellitus, Immune-mediated (0.9% to 1.5%)
- **Gastrointestinal:** Colitis, Immune-mediated (Monotherapy, 2.9%; combined with ipilimumab, 26%), Diarrhea (17% to 52%), Duodenitis, Immune-mediated (Less than 1%), Gastritis, Immune-mediated (Less than 1%), Pancreatitis, Immune-mediated (Less than 1%), Perforation of colon (Less than 10%)
- **Hematologic:** Anemia, Grade 3 or 4 (1.1% to 8%), Lymphocytopenia, Grade 3 or 4 (4.3% to 9%), Neutropenia, Grade 3 or 4 (1.1%)
- **Hepatic:** Hepatitis, Immune-mediated (1.8% to 13%)
- **Immunologic:** Histiocytic necrotizing lymphadenitis, Immune-mediated (Less than 1%), Sarcoidosis, Immune-mediated (Less than 1%)
- **Musculoskeletal:** Eaton-Lambert syndrome, Immune-mediated (Less than 1%), Myositis, Immune-mediated (Less than 1%), Rhabdomyolysis, Immune-mediated (Less than 1%)
- **Neurologic:** Demyelination of spinal cord, Immune-mediated (Less than 1%), Encephalitis, Immune-mediated (0.2%), Guillain-Barré syndrome, Immune-mediated (Less than 1%), Neuropathy, Immune-mediated (Less than 1%)
- **Ophthalmic:** Uveitis, Immune-mediated (Less than 1%)
- **Renal:** Nephritis, Immune-mediated, Renal impairment, Immune-mediated, Urinary tract infectious disease (Urothelial carcinoma, 17%)
- **Respiratory:** Pleural effusion (2% or greater), Pneumonitis, Immune-mediated (3.1% to 6%), Pulmonary embolism (Non-small cell lung cancer, 4.2%), Respiratory failure (2% or greater), Respiratory tract infection (2% or greater)
- **Other:** Sepsis (2% or greater)

Atezolizumab

Common

- **Gastrointestinal:** Constipation (15% to 21%), Decrease in appetite (24% to 35%), Diarrhea, Immune-mediated (18% to 24%), Nausea (22% to 25%)
- **Respiratory:** Cough (14% to 30%), Dyspnea (12% to 32%)
- **Other:** Fatigue (52%)

Serious

- **Cardiovascular:** Myocarditis (Up to 1%)
- **Endocrine metabolic:** Adrenal insufficiency, Immune-mediated (0.4%), Diabetes mellitus, Immune-mediated (0.2% to 0.3%), Hyperthyroidism (0.6% to 1.1%), Hypophysitis, Immune-mediated (0.2%), Hypothyroidism (2.5% to 4.2%)
- **Gastrointestinal:** Abdominal pain (15% to 17%), Colitis, Immune-mediated, Pancreatitis, Immune-mediated (0.1%)
- **Hepatic:** Hepatitis, Immune-mediated (0.9% to 1.3%)
- **Musculoskeletal:** Eaton-Lambert syndrome, Myasthenia gravis, Immune-mediated
- **Neurologic:** Encephalitis, Guillain-Barré syndrome, Immune-mediated, Meningitis
- **Renal:** Hematuria (14%), Urinary tract infectious disease (17% to 22%)
- **Respiratory:** Interstitial lung disease, Pneumonitis, Immune-mediated
- **Other:** Fever (14% to 21%), Infectious disease (37.7% to 43%), Infusion reaction (1.6% to 1.7%)

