6.2 Immune Checkpoint Blockade Therapy

All patients will continue treatment with their prior anti-PD1 or anti-PDL1 antibody treatment as per standard of care.

Dose delays or modifications for the ICB agent will be per standard of care and independent of exemestane therapy. A summary of the expected toxicity for each of the three possible ICB agents is provided in Appendix IV.

ICB therapy will be obtained through the same mechanism and will continue to be charged to the patient and her third party payer as before study enrollment.

If the ICB therapy is delayed, exemestane therapy should continue as medically appropriate.

Exemestane may be continued at the discretion of the treating investigator if the ICB therapy is permanently discontinued.

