10.2.2 Event Documentation

Adverse events occurring after the initiation of exemestane treatment through and including 28 calendar days after the last dose must be documented. Refer to Section 6.1.1 for a list of expected toxicities of exemestane and Appendix IV for a list of expected toxicities for the ICB therapy.

Since a key outcome parameter of this study is to characterize the toxicities of exemestane in combination with an FDA approved immune checkpoint inhibitor in this patient population, adverse event documentation requirements will be

determined based on grade, expectedness and relationship to study therapy as follows:

	CTCAE Grade 1	CTCAE Grade 2		CTCAE Grade 3		CTCAE Grade 4 and 5
	Expected or Unexpected	Expected	Unexpected	Expected	Unexpected	Expected or Unexpected
Unrelated Unlikely	Not required	Not required	Not required	Not required	Required	Required
Possible Probable Definite	Not required	Not required	Required	Required	Required	Required

In addition any event meeting the definition of a serious adverse event (SAE) regardless of attribution that occurs during this period will be documented in the source document and recorded in OnCore.

After the end of treatment visit, monitoring for adverse event will become less frequent based on the schedule in Section 9 and only events at least possibly related to study treatment (based on the table above) will be documented upon knowledge.

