13.1 Study Design, Objectives and Endpoints

The goal of this phase II study is to estimate the probability of response after treatment of exemestane in post-menopausal women with advanced non-small cell lung cancer progressing while on immune checkpoint blockade. The primary endpoint of treatment response will be assessed at 6 weeks after the start of treatment using RECIST criteria. Secondary endpoints include the proportion of toxicities through 30 days after the last dose or start of new treatment as described in Section 10.2.2, disease-control as measured by response duration, progression-free and overall survival through 12 months from study enrollment and quality of life scores as measured by PROMIS-29 at baseline, every 3 weeks during treatment and at the end of treatment visit. The primary endpoint of response will be evaluated using a two-stage design.

Stage 1 will enroll 10 patients. If 2 or more patients have an objective response after completion of stage 1, an additional 19 patients will be enrolled in stage 2 for a total of 29 patients. If the total number of patients responding is 4 or greater, the treatment will be considered worthy of further investigation.

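### The plan does not fix one reference for an expected event, so recording of some Grade 2 and Grade 3 immune events either varies by antibody or is not required for anyone

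*Combined protocol and SAP*

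**What the plan says.** Section 10.2.2 says that documentation requirements are "determined based on grade, expectedness and relationship to study therapy as follows" and gives a table. For the antibodies it points to "Appendix IV for a list of expected toxicities for the ICB therapy". Section 6.2 describes that appendix in these words: "A summary of the expected toxicity for each of the three possible ICB agents is provided in Appendix IV". The appendix has three separate lists, for pembrolizumab, nivolumab and atezolizumab. The nivolumab list includes "Hyperthyroidism, Immune-mediated (2.7% to 8%), Hypophysitis, Immune-mediated (0.6% to 9%), Hypopituitarism, Immune-mediated (Less than 1%), Hypothyroidism, Immune-mediated". The serious endocrine line for pembrolizumab contains hypophysitis alone.

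Section 10.1 defines expectedness differently. An event is unexpected if protocol-related documents (the protocol, consent documents and package insert are among the examples) do not list it, or do not list it at the specificity or severity observed. Section 10.1 also says that the drug meant throughout Section 10 is exemestane, and it defines attribution against the study drug. Section 12.2 says that expectedness and attribution for the toxicity endpoint follow Section 10.1.

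The endpoint leads back to the recording rule. Section 13.1 states: "Secondary endpoints include the proportion of toxicities through 30 days after the last dose or start of new treatment as described in Section 10.2.2". Section 13.3 summarises toxicities as simple proportions and bar graphs, with no split by antibody. Section 10.2.2 itself treats the toxicity of the combination as a central outcome of the study.

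**The concern.** A toxicity proportion can be interpreted only if the rule for entering the numerator is the same for every patient in the denominator. Here the rule depends on a word, expected, that has two possible references. One is a set of antibody-specific lists taken from a drug reference. The other is the protocol-related documents as a whole. They give different answers for common immune events, and sites could choose differently.

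The events concerned matter to the study's question. Section 2.2 argues that exemestane should reverse immunosuppression, while Section 6.1.1 expects no change in the toxicity profile when it is added to an antibody. Non-serious Grade 2 immune events are part of the evidence that would test that expectation. In the affected cells, a low or zero count could not be read as absence of the event.

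**Working it through.** The documents state no figure for this point, so the check sets the passages side by side.

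**Step 1. Where expectedness matters (table in Section 10.2.2).** Entries show whether documentation is required if the event is expected / unexpected.

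| Grade | Unrelated or unlikely | Possible, probable or definite |
|---|---|---|
| 1 | no / no | no / no |
| 2 | no / no | **no / yes** |
| 3 | **no / yes** | yes / yes |
| 4 | yes / yes | yes / yes |
| 5 | yes / yes | yes / yes |

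Five grades times two attribution groups give 10 cells, of which 2 change with expectedness. Two other rules narrow these further. Section 10.2.2 requires all serious adverse events to be recorded regardless of attribution. Section 10.3 requires Grade 3 to 5 immune-related pneumonitis, colitis, nephritis, myocarditis and hepatitis to be reported as stopping-rule events. What remains is non-serious related Grade 2 events, and non-serious unrelated or unlikely Grade 3 events other than those five conditions.

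**Step 2. What the lists contain (Appendix IV, common and serious entries together).**

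| Event | Pembrolizumab | Nivolumab | Atezolizumab |
|---|---|---|---|
| Hypothyroidism, hyperthyroidism, adrenal insufficiency, diabetes, colitis, myocarditis | not listed | listed | listed |
| Rash, pruritus, nephritis, raised AST | listed | listed | not listed |
| Pneumonitis, hepatitis, hypophysitis | listed | listed | listed |

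The exemestane list in Section 6.1.1 contains none of the events in the first two rows, so it does not close the gaps.

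**Step 3. The two readings applied to non-serious events.** Related means at least possibly related to exemestane.

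| Event | Judged by the patient's own antibody list | Section 10.1 read literally |
|---|---|---|
| Related Grade 2 hypothyroidism | required on pembrolizumab only | required for no one |
| Related Grade 2 rash | required on atezolizumab only | required for no one |
| Grade 3 adrenal insufficiency, unlikely related | required on pembrolizumab only | required for no one |
| Grade 2 hypothyroidism attributed to the antibody alone | required for no one | required for no one |

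The last row follows from attribution being defined against exemestane: the event falls in the unrelated or unlikely row, where Grade 2 is never required.

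**Step 4. Size.** Let q be the true rate of an event in an affected cell, assumed equal across antibodies, and s the share of patients on antibodies whose list omits it. Under the first reading the rate that must be recorded is q × s; under the second it is 0. The documents do not give the antibody mix, so s can lie anywhere from 0 to 1. For scale only, with assumed q of 5%, 10% or 15% and all 29 patients, the events number 29 × 0.05 = 1.45, 29 × 0.10 = 2.90 or 29 × 0.15 = 4.35. The number that must be recorded lies between none and all of them. The q values are not estimates from the documents.

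**The case against.** The strongest reply is that Section 10.1 controls. Section 12.2 names it, Appendix IV is part of the protocol, and nothing says that expectedness is judged only against the patient's own antibody. Package inserts also count and are not available here, so absence from an Appendix IV list does not prove that an event is unexpected. This stands as far as it goes: a difference between antibodies is one reading, not the settled text. It does not remove the problem, because under the literal reading the same related Grade 2 events need not be recorded for any patient. The clause on specificity and severity in Section 10.1, and the agent-by-agent layout described in Section 6.2, keep the other reading open.

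It is also fair to say that toxicity is a descriptive secondary endpoint in at most 29 patients, that no comparison between antibodies is planned, and that a filter based on expectedness is a stated choice. A table entry of not required does not forbid recording, and Section 9.1 has symptoms and toxicity noted every 3 weeks. These points limit the consequence. They do not make the filter uniform, and voluntary entries do not give a usable proportion.

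A reader might infer that, outside serious events and stopping-rule conditions, immune toxicity in general is recorded on one antibody and lost on another. The documents do not support that. The table itself requires all related Grade 3 and all Grade 4 and 5 events whatever the expectedness. Nor do the unequal lists weaken the stopping rules: Sections 10.3 and 13.4 do not use expectedness.

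**Conclusion.** The concern holds in a limited form. Sections 10.1, 10.2.2 and 12.2 and Appendix IV do not fix one expectedness reference, and two documentation cells depend on it. In those cells recording either varies by antibody or, for the listed events, is required for no one. The toxicity proportions in Sections 13.1 and 13.3 are then incomplete for these events.

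The number of events lost cannot be derived from the documents. It depends on the antibody mix, the true rates, the attribution judgements and the reading each site adopts. A particular fraction would rest on assumed inputs and should not be cited as a finding. The primary response endpoint, the toxicity stopping boundaries, serious events, related Grade 3 events and all Grade 4 and 5 events are not affected. This is an inexpensive improvement to a secondary endpoint, not a flaw in the main inference.

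**What to change.** - In Section 10.2.2, require documentation of all immune-related events of Grade 2 or higher, regardless of expectedness, attribution and antibody. State which events count as immune-related; a single set drawn from all three Appendix IV lists would serve.
- For all other events, name one expectedness reference that applies to every patient whichever antibody she receives, and word it consistently in Sections 10.1, 10.2.2 and 12.2. Entries such as pruritus or raised AST would fall here if they are not classed as immune-related.
- In Section 13.3, show toxicity proportions by antibody as well as pooled, with the number of patients on each antibody.

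A lighter change would be to call an event expected only if all three lists name it. That makes recording uniform, but it leaves related Grade 2 pneumonitis, hepatitis and hypophysitis undocumented for everyone and gives unexpected a meaning that conflicts with Section 10.1.

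The cost is consistent wording in three sections, one line in the analysis section, and a few more event entries in at most 29 patients. No change to sample size, visits or stopping boundaries is needed.
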